## 7.2 Assessment types

### 7.2.1 Efficacy assessments

#### 7.2.1.1 Mean urinary free cortisol (mUFC)

The primary efficacy parameter will be the proportion of patients who attain mUFC  $\leq 1.0$  ULN at week 35 with pasireotide alone or in combination with cabergoline.

Screening urinary free cortisol will be measured in three 24-hour urine specimens collected during the screening period 24-h urine collections will have to be performed within the first 8 to 10 days of the screening period so that to have 24h-UFC results available before visit 2 (baseline visit). The 24h-UFC concentration results from these three samples will be averaged to obtain the baseline urinary free cortisol level. During the study, mean 24h-UFC will be determined at 4 week interval in the core phase and at 8 week interval in the extension phase.

In the core phase of the study, patients at weeks 4, 8, 13, 17, 22, 26, 31 and 35, mean 24h-UFC will be determined from two 24-hour urine collections collected on two consecutive days occurring before the visit. In the extension phase of the study, patients' 24h-UFC will be determined at 8 week interval, at weeks 43, 51, 59, 67, 75 and so on. The 24h-UFC will continue to be determined from two 24-hour urine collections collected from two consecutive days occurring before the visit in the extension phase until patient is discontinued from treatment.

#### **7.2.1.2 Serum cortisol**

A pre-dose blood draw for an 8 am fasting serum cortisol measurement will be taken at visits indicated in [Table 7-1](#) and [Table 7-2](#). Procedures for sample drawing, handling, storage and transportation will be provided by the central laboratory.

#### **7.2.1.3 Late night salivary cortisol**

Late night salivary cortisol will be determined at visits indicated in [Table 7-1](#) and [Table 7-2](#).

Patients should be given instructions and supplies for use at home. In order to correlate the salivary and urinary cortisol results, a single salivary sample per evening is to be collected on the same evenings as the first 2 of the 3 twenty-four hour urinary collections for UFC for a total of 2 salivary samples as indicated in [Table 7-1](#) and [Table 7-2](#). One sample per evening is to be taken at 11 PM (23:00) with a +/- 1 hour window. All efforts should be made to have the samples taken at the same time throughout the study. Samples are to be collected by the site at the same time as the UFC samples as described in [Table 7-1](#) and [Table 7-2](#).

#### **7.2.1.4 Plasma ACTH**

A pre-dose blood draw for plasma ACTH sampling will be taken at visits indicated in [Table 7-1](#) and [Table 7-2](#). Procedures for sample drawing, handling, storage and transportation will be provided by the central laboratory.

[figure not shown]
#### **7.2.1.5 Continuous measures of clinical symptoms of hypercortisolism**

The following clinical symptoms will be assessed:

##### **Manual Blood pressure:**

Sitting and standing blood pressure will be recorded at every indicated visit. The arm in which the highest sitting pressures are found at screening will be the arm used for all subsequent readings throughout the study. If there is a discrepancy between the arms regarding the highest systolic and diastolic value, the arm with the highest mean blood pressure will be used according to the following formula: mean BP = DBP + [(SBP – DBP)/3]. All attempts should be made to have the same individual obtain blood pressure readings from each individual patient at each visit at the same time of the day with the same equipment.

Arterial blood pressure determinations will be made in accordance with the (1988 AHA Committee Report) on blood pressure determination (Circulation 88: 2460-2467, 1993). With the arm supported at the level of the heart, systolic pressure will be recorded when the initial sound is heard (Phase I of the Korotkoff sound); diastolic pressure will be recorded at the disappearance of the sound (Phase V of the Korotkoff sound). At each study visit, after having

the patient in a sitting position for five minutes, systolic/diastolic blood pressure will be measured three times. The systolic/diastolic blood pressure will then be measured in a standing position three times. The repeat measurements are to be made at least at 5-minute intervals. No up-and-down rounding is allowed. The mean of all three sitting measurements is decisive for study specific procedures.

**Weight:** Body weight will be measured at every indicated visit using a calibrated balance. The balance should be placed on a hard flat surface, and checked for zero balance before each measurement. The patient should stand unassisted, in the center of the platform, and be asked to look straight ahead, standing relaxed but still. The patient should wear light underclothing and/or a paper examining gown and paper slippers. Shoes and socks should not be worn.

**Body mass index (BMI):**

BMI will be derived from the height and weight measurements

**Waist circumference:** Waist circumference will be measured at visits indicated in [Table 7-1](#) and [Table 7-2](#). Patients should remove clothing from around the waist to ensure the measuring tape is correctly positioned. Using a cosmetic pencil, make a mark at the “natural waist” midway between the palpated iliac crest and the palpated lowest rib margin in the left and right mid-axillary lines. Place the non-stretchable tape evenly around the natural waist covering the left and right natural-waist marks. The measurement scale should face outward, and there should be no twists in the tape. Ensure that the tape is just touching the skin but not compressing the soft tissue. Instruct patients to stand erect with abdomen relaxed, arms at sides, feet together, and weight divided equally over both legs.

#### **7.2.1.6 Categorical measures of clinical signs of hypercortisolism**

The results of all the following assessments will be recorded in the CRF.

The following symptoms will be evaluated using photographs taken at visits in the core and extension phases as indicated in [Table 7-1](#) and [Table 7-2](#):

**Facial rubor, hirsutism, striae, and supraclavicular and dorsal fat pad.** Two photographs, one frontal and one lateral from the shoulders up will be taken to assess facial plethora, supraclavicular and dorsal fat pads. Two photographs, frontal and dorsal of the trunk with patient in standing position will be taken to assess striae, and hirsutism. The photographs must be assessed by a qualified physician at the site, who is blinded to the dose given to the patient and to the time point at which the photographs were taken. Consisting with confidentiality requirements these will not be published without explicit written permission by the patient.

For further assessment of hirsutism, the Ferriman-Gallywey score (see [Appendix 5](#)), a method of evaluating and quantifying hirsutism in women, will be used. Female patients will be asked not to shave or use any methods of hair removal during the 3 weeks prior to corresponding visits if possible.

## **Muscle strength**

To test proximal muscle strength patients should be placed in a low seated position (for instance on an examination room stool). They should be asked to extend the arms in front of them. From this seated position patients will be asked to stand up. Patients will be evaluated using the following scale:

3. - completely unable to stand
2. - able to stand only by using arms as assistance
1. - able to stand after several efforts without using arms as assistance
0. - able to stand easily with arms extended

### **7.2.1.7 Health-related quality of life (HRQOL)**

The health-related quality of life will be assessed for patients using the Cushing QoL and SF-12v2 General Health Survey (see [Appendix 2](#) and [Appendix 3](#)), a patient-reported outcome instrument specific to patients with Cushing's syndrome. The questionnaires will be completed at visits indicated in [Table 7-1](#) and [Table 7-2](#).

## **7.2.2 Safety and tolerability assessments**

Safety will be monitored by assessing Physical examination, karnofsky performance status, vital signs, Laboratory assessments (hematology, chemistry, including LFTs, coagulation, urinalysis, hormone assessments, fasting blood glucose, HbA1C, GH and IGF-1), gallbladder ultrasound, and ECG as well as collecting of the adverse events at every visit.

### **7.2.2.1 Physical examination**

[figure not shown]
A complete physical examination will be performed by the investigator at screening visits indicated in [Table 7-1](#) and [Table 7-2](#). An abbreviated physical examination will be performed at the subsequent visits indicated [Table 7-1](#) and [Table 7-2](#). Information about the physical examination findings will be presented in the source documentation at the study site. Significant findings that were present prior to the signing of informed consent must be included in the Relevant Medical History/Current Medical Conditions page on the patient's CRF. Significant new findings that begin or worsen after informed consent must be recorded on the Adverse Event page of the patient's CRF.

### **7.2.2.2 Vital signs**

Blood pressure, body temperature and heart rate will be measured visits indicated in [Table 7-1](#) and [Table 7-2](#) and recorded in the appropriate CRF.

### **7.2.2.3 Height and weight**

Height in centimeters (cm) and weight to the nearest 0.1 kilogram [kg] are to be collected at visits indicated in [Table 7-1](#) and [Table 7-2](#) and recorded in the appropriate CRF.

#### 7.2.2.4 Karnofsky performance status

The Karnofsky performance scale index (see [Appendix 1](#)) will be used to evaluate the performance status of the patients at visits indicated in [Table 7-1](#) and [Table 7-2](#).

#### 7.2.2.5 Laboratory evaluations

Central laboratories will be used for the analysis of all laboratory evaluations. Details on the collections, shipment of samples and reporting of results by the central laboratory are to be provided to investigators in the [\[Laboratory Manual\]](#).

##### 7.2.2.5.1 Hematology

Hematocrit, Hemoglobin, MCH, MCHC, MCV, Platelets, Red blood cells, White blood cells, RBC Morphology with Differential (Basophils, Eosinophils, Lymphocytes, Monocytes, Neutrophils)

##### 7.2.2.5.2 Clinical chemistry

GGT, calcium, urine creatinine, creatine kinase, amylase, lipase, total cholesterol, LDL-cholesterol, HDL-cholesterol, total protein, triglycerides, blood urea nitrogen (BUN) or urea, uric acid, magnesium, sodium, potassium, serum creatinine, estimated glomerular filtration rate from serum creatinine (at screening and end of treatment only), fasting blood glucose and glycosylated hemoglobin (HbA1C).

The following Modification of Diet in Renal Disease (MDRD) will be used for creatinine clearance calculation:

MDRD (GFR) (ml/min/1.73m^2) = 175 \* PD93 power -1.154 \* Age power - 0.203 \* Race \* Sex Where PD93 = Serum Creatinine (mg/dL), Race = 1.212 for Black & 1.000 for other, Sex = 1.00 for males and 0.742 for females.

SI Results MDRD (GFR) (ml/min/1.73m^2) = 175 \* (PD9S3/88.4) power -1.154 \* Age power - 0.203 \* Race \* Sex Where PD9S3 = Serum Creatinine (UMOL/L), Race = 1.212 for Black & 1.000 for other, Sex = 1.00 for males and 0.742 for females.

##### 7.2.2.5.3 Liver function testing

Presence of HbsAg and Anti-HCV are to be assessed during screening. Liver function tests (LFTs) will be measured: ALT, AST, total bilirubin, direct bilirubin, indirect bilirubin, Albumin, ALP and GGT. If at any visit abnormal liver function criteria as described in the inclusion and exclusion section are met, the following should be performed immediately within 48 hours of awareness of the abnormality. Liver function tests (LFTs) should be monitored every 3-4 days until resolution or return to baseline status. Please refer to [Section 6.5.4 Hepatic Safety Management](#).

Perform hepatitis screen: anti-HAV, IgM (to confirm acute Hepatitis A), HbsAg, Anti-HBc, anti-HCV (if positive, PCR viral load should be assessed), Anti-HEV, ANA antibodies, anti-smooth muscle anti-bodies, CMV and EBV.

#### 7.2.2.5.4 Coagulation

PT and INR will be measured at visits indicated in [Table 7-1](#) and [Table 7-2](#).

#### 7.2.2.5.5 Additional hormones

Midnight salivary cortisol, Urine free cortisol (UFC), Insulin-like growth factor 1 (IGF-1), GH, Free T4, and TSH, serum cortisol, Plasma ACTH

#### 7.2.2.5.6 Urinalysis

A urinalysis test (specific gravity, pH, glucose, proteins, bilirubin, ketones, leucocytes, color, nitrite and blood) will be analyzed at visits indicated in [Table 7-1](#) and [Table 7-2](#). The 24 hour urinary collections used for mUFC will also be used to collect urine volume, and urinary creatinine.

#### 7.2.2.5.7 Pregnancy and assessments of fertility

All pre-menopausal women who are not surgically sterile will have a urine dip-stick pregnancy test at visits indicated in [Table 7-1](#) and [Table 7-2](#). A serum  $\beta$ -hCG pregnancy test must be performed if the urine dip-stick pregnancy test is positive. A positive serum pregnancy test requires immediate interruption of study treatment until the assessment is confirmed. If positive, the patient must be discontinued from the study.

#### 7.2.2.5.8 Gallbladder ultrasound

A gallbladder ultrasound will be performed at the sites at visits indicated in [Table 7-1](#) and [Table 7-2](#) and the results will be recorded in the CRF.

#### 7.2.2.5.9 Cardiac assessments

##### Electrocardiogram (ECG)

A 12-lead ECG and a rhythm strip will be performed at the sites at visits indicated in [Table 7-1](#) and [Table 7-2](#). All ECGs should include all 12 standard leads and a Lead II rhythm strip of at least a 10- second duration. The ECGs will be performed on the machine(s) provided for the study by the central reader and are sent to the central reader for evaluation. To ensure consistency throughout all participating sites, the ECGs should be performed and processed following the guidelines from the central reading facility, which will be distributed to the sites. A Holter ECG will be required in case of a confirmed QTcF  $> 480$ msec (described in [Section 6.5.3](#)).

#### 7.2.2.5.10 Echocardiogram

An echocardiogram will be performed at the visits indicated in [Table 7-1](#) and [Table 7-2](#).

## 8 Safety monitoring and reporting

### 8.1 Adverse events

#### 8.1.1 Definitions and reporting

An adverse event is defined as the appearance of (or worsening of any pre-existing) undesirable sign(s), symptom(s), or medical condition(s) that occur after patient's signed informed consent has been obtained. Abnormal laboratory values or test results occurring after informed consent constitute adverse events only if they induce clinical signs or symptoms, are considered clinically significant, require therapy (e.g., hematologic abnormality that requires transfusion or hematological stem cell support), or require changes in study medication(s).

Adverse events that begin or worsen after informed consent should be recorded in the Adverse Events CRF. Conditions that were already present at the time of informed consent should be recorded in the Medical History page of the patient's CRF. Adverse event monitoring should be continued for at least 30 days following the last dose of study treatment. Adverse events (including lab abnormalities that constitute AEs) should be described using a diagnosis whenever possible, rather than individual underlying signs and symptoms. When a clear diagnosis cannot be identified, each sign or symptom should be reported as a separate Adverse Event.

Adverse events will be assessed according to the Common Terminology Criteria for Adverse Events (CTCAE) version 4.03. If CTCAE grading does not exist for an adverse event, the severity of mild, moderate, severe, and life-threatening, corresponding to Grades 1 - 4, will be used. CTCAE Grade 5 (death) will not be used in this study; rather, information about deaths will be collected through a Death form.

The occurrence of adverse events should be sought by non-directive questioning of the patient during the screening process after signing informed consent and at each visit during the study. Adverse events also may be detected when they are volunteered by the patient during the screening process or between visits, or through physical examination, laboratory test, or other assessments. As far as possible, each adverse event should be evaluated to determine:

1. The severity grade (grade 1-4)
2. Its duration (start and end dates or Ongoing at End of Study)
3. Its relationship to the study treatment (Reasonable possibility that AE is related: No, Yes)
4. Action taken with respect to study or investigational treatment (none, dose adjusted, temporarily interrupted, permanently discontinued, unknown, not applicable)
5. Whether medication or therapy was given (no concomitant medication/non-drug therapy, concomitant medication/non-drug therapy)
6. Whether it is serious, where a serious adverse even (SAE) is defined as in [Section 8.2.1](#)

All adverse events should be treated appropriately. If a concomitant medication or non-drug therapy is given, this action should be recorded on the Adverse Event CRF.

Once an adverse event is detected, it should be followed until its resolution or until it is judged to be permanent, and assessment should be made at each visit (or more frequently, if

necessary) of any changes in severity, the suspected relationship to the study treatment, the interventions required to treat it, and the outcome.

All adverse events, regardless of the severity, should be reported. This will also include any adverse events that meet the definition of special interest.

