Study treatment	Includes any drug or combination of drugs in any study arm administered to the patient (subject) as part of the required study procedures, including placebo and active drug run-ins. In specific examples, it is important to judge investigational treatment component relationship relative to a study treatment combination; study treatment in this case refers to the investigational and non-investigational treatments in combination.
Study treatment discontinuation	Point/time when patient permanently stops taking study treatment for any reason; may or may not also be the point/time of premature patient withdrawal
Patient group	A treatment group defines the dose and regimen or the combination, and may consist of 1 or more cohorts. Cohorts are not expanded, new cohorts are enrolled.
Variable	Identifier used in the data analysis; derived directly or indirectly from data collected using specified assessments at specified time points.

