**Table 6-4 Guidelines for treatment of patients experiencing adverse events**

Patients	Adverse Event	Action
All	AE grade $\leq$ 2 (mild to moderate)	No drug adjustments
	AE grade $\geq$ 3 (severe to life-threatening) and judged as pasireotide-related	Reduce dose of by 0.3mg bid. If AE improves to grade $\leq$ 2 within 1 week, increase dose by 0.3mg bid. If AE recurs at grade $\geq$ 3, reduce dose by 0.3mg bid again and remain at lower dose. If AE does not improve to grade $\leq$ 2 within 1 week on lower dose, reduce dose by 0.3mg bid again if possible. If AE does not improve to grade $\leq$ 2 within 1 week on 0.3mg bid patient should be discontinued from study treatment
	AE grade $\geq$ 3 (severe to life-threatening) and judged as cabergoline-related	Reduce dose from daily schedule to every other day schedule. If AE improves to grade $\leq$ 2 within 1 week, increase dose to daily schedule. If AE recurs at grade $\geq$ 3, reduce dose every other day schedule again and remain at that schedule. If AE does not improve to grade $\leq$ 2 within 1 week on the every other day schedule, patient should be discontinued from study treatment
	All patients	For patients experiencing hyperglycemia, the dose should be reduced if severity grade 3 or greater persists despite appropriate management. If the hyperglycemia is considered to be life-threatening, the patient should be withdrawn from study treatment regardless of anti-diabetes treatment
	AE grade 3 – All patients	NCI-CTCAE v4.03 grades diabetes that is treated with insulin as a grade 3. However, diabetes grade 3 will require a study drug dose reduction only in cases of uncontrolled hyperglycemia despite appropriate management. Patients who despite appropriate therapeutic interventions and dose reduction of study drug, develop uncontrolled diabetes and/or consistently high blood glucose values: FPG $\geq$ 240mg/fdL (13.3 mmol/L) or HbA1c value $\geq$ 10% will require study treatment discontinuation
	Hypocortisolism	If a patient shows high sensitivity to pasireotide 0.6 mg bid resulting in cortisol values $<$ LLN and/or signs/symptoms consistent with the diagnosis of hypocortisolism, the dose of pasireotide can be decreased to 0.3 mg bid. Despite the dose reduction, some patients may still present with cortisol values $<$ LLN and/or signs/symptoms consistent with hypocortisolism; in this case the dose of pasireotide can be further reduced to 0.3 mg qd in order to achieve and maintain normal cortisol levels.

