### **8.2.2 Reporting**

To ensure patient safety, every SAE, regardless of suspected causality, occurring after the patient has provided informed consent and until 30 days after the patient has stopped study treatment must be reported to Novartis within 24 hours of learning of its occurrence. Any SAEs experienced after this 30 days period should only be reported to Novartis if the investigator suspects a causal relationship to the study treatment. Recurrent episodes, complications, or progression of the initial SAE must be reported as follow-up to the original episode within 24 hours of the investigator receiving the follow-up information. An SAE occurring at a different time interval or otherwise considered completely unrelated to a previously reported one should be reported separately as a new event.

Information about all SAEs is collected and recorded on the Serious Adverse Event Report Form. The investigator must assess and record the relationship of each SAE to each specific study treatment (if there is more than one study treatment), complete the SAE Report Form in English, and send the completed, signed form by fax within 24 hours to the Novartis Chief Medical Office and Patient Safety (CMO&PS).

Detailed instructions regarding the SAE submission process and requirements for signatures are to be found in the investigator folder provided to each site. The original copy of the SAE Report Form and the fax confirmation sheet must be kept with the case report form documentation at the study site.

Follow-up information is sent to the same contact(s) to whom the original SAE Report Form was sent, using a new SAE Report Form stating that this is a follow-up to the previously reported SAE and giving the date of the original report. Each re-occurrence, complication, or progression of the original event should be reported as a follow-up to that event regardless of when it occurs. The follow-up information should describe whether the event has resolved or continues, if and how it was treated, and whether the patient continued or withdrew from study participation.

If the SAE is not previously documented in the Investigator's Brochure or Package Insert (new occurrence) and is thought to be related to the Novartis study treatment, an oncology Novartis Chief Medical Office and Patient Safety (CMO&PS) department associate may

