6.6.1 Adverse events (AE)

All adverse events and the cause of death, as recorded on the completion CRF pages, will be coded using the latest available version of the MedDRA coding dictionary that provides the system organ class (SOC) and preferred term (PT) information.

AEs will be graded according to the Common Terminology Criteria for Adverse Events (CTCAE) version 4.0.

The CTC/severity grade will not be imputed if missing. CTC grade 5 (death) will not be used in this study.

The incidence of treatment-emergent AEs, during the core phase and during the overall on- treatment period, will be summarized by system organ class (SOC), preferred term (PT) and severity (based on NCI-CTCAE v.4 grades), type of adverse event, relation to study treatment.

A patient with multiple occurrences of an AE will be counted only once in the respective AE category

The following selection of treatment-emergent AEs will be listed and summarized for safety set from study start to final cut-off date for safety set:

- AEs regardless of study drug relationship
- AEs suspected to be study drug-related
- SAEs regardless of study drug relationship
- AEs leading to study drug discontinuation, regardless of study drug relationship
- AEs leading to study drug discontinuation, suspected to be study drug-related
- AEs requiring dose adjustment or study-drug interruption, regardless of study drug relationship
- AEs requiring additional therapy, regardless of study drug relationship
- AEs excluding SAEs
- Adverse events of special interest by type

Specific groupings of AEs of special interest will be considered and the number of patients with at least one event in each grouping ("category") will be reported. Such groups consist of AEs for which there is a specific clinical interest in connection with pasireotide treatment (i.e. where pasireotide may influence a common mechanism of action responsible for triggering them) or AEs which are similar in nature (although not identical) within safety set. The specific groupings of AEs as defined in the latest documentation available prior to database lock (in [[Cabinets/CREDI Projects/S/SOM230B/Integrated Medical Safety/Safety Profiling and Signal detection/Signal detection]]).

The following table will be produced:

- AEs of special interest by type (any AE, AE suspected to be drug-related, SAE, AE leading to discontinuation, AE requiring dose adjustment), PT and maximum Common Terminology Criteria (CTC) grade.

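### Protocol 8.1.1 and the SAP neither require nor tabulate per-drug causality for non-serious AEs on the combination, although the grade 3 or higher dose rules and SAE reporting depend on it

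*Protocol*

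**What the plan says.** Protocol 8.1.1 lists what the investigator should determine for every AE. Item 3 is one yes/no causality judgement: "Its relationship to the study treatment (Reasonable possibility that AE is related: No, Yes". Item 4 is one item on what was done: "Action taken with respect to study or investigational treatment". At follow-up visits the same unit is used again: "the suspected relationship to the study treatment, the interventions required to treat it, and the outcome". For a combination regimen, the glossary says that "study treatment in this case refers to the investigational and non-investigational treatments in combination".

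Two other parts of the protocol work drug by drug:

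- **Dose rules.** Table 6-4 has one path for grade 3 or higher events "severe to life-threatening) and judged as pasireotide-related" and a different one for those "severe to life-threatening) and judged as cabergoline-related". The text of section 6.6 also acts on toxicity that the investigator attributes to pasireotide.
- **Serious events.** Section 8.2.2 states: "The investigator must assess and record the relationship of each SAE to each specific study treatment (if there is more than one study treatment".

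The analyses return to the undivided unit. Protocol 10.3.1.2 summarises AEs by relation to study treatment. SAP 6.6.1 lists "AEs suspected to be study drug-related", together with study-drug discontinuation and dose adjustment or interruption, none of them split by drug. It plans SAEs only regardless of relationship, so the per-drug SAE causality that 8.2.2 asks for is not tabulated either.

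**The concern.** The safety of pasireotide alone or with cabergoline is a secondary objective (Table 3-1, objective 9). Under Table 6-4 the investigator must decide which drug is responsible for a severe event before acting. Yet the protocol's list of AE items does not ask for that decision to be recorded unless the event is serious.

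The study report could then give the number of patients on the combination with a related AE, or an AE leading to dose adjustment, without separating suspicion of pasireotide from suspicion of cabergoline. Tolerability under 10.3.1.5, defined by dose reductions and interruptions due to an AE, could not be read by drug from the AE data alone. Nor could those data show which path of Table 6-4 a patient was meant to follow.

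**Working it through.** The plan gives no figure on this point to reproduce. The check is a comparison of the sections, followed by a rough count of the patients concerned.

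**Step 1. Unit of causality in each place**

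| Place | Events | Causality unit |
|---|---|---|
| Protocol 8.1.1, items 3 and 4 | All AEs | Study treatment, one answer each |
| Protocol 6.6 | Grade 3 or higher | Pasireotide |
| Protocol Table 6-4 | Grade 3 or higher | Pasireotide or cabergoline |
| Protocol 8.2.2 | SAEs | Each drug |
| Protocol 10.3.1.2 | Treatment-emergent AEs | Study treatment |
| SAP 6.6.1 | Treatment-emergent AEs | Study drug |

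Per-drug causality is needed in 6.6, Table 6-4 and 8.2.2. It is absent from the AE item list and from both analysis sections.

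**Step 2. Where the dose rules and the AE record collide**

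- On pasireotide monotherapy only one drug is given, so causality for the regimen is causality for pasireotide.
- SAEs carry per-drug causality under 8.2.2.
- Grade 2 or lower events call for no drug adjustment under Table 6-4.
- What remains is non-serious grade 3 or higher events during combination treatment.

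The gap in description is wider than the conflict with the dose rules: it covers all non-serious AEs on the combination.

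**Step 3. What can be recovered**

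Protocol 6.3.4 requires every dose change to be entered on the dosage administration CRF. Protocol 10.2.1 lists planned and actual doses with the reason for each change. SAP 6.4.1 and 6.4.2 derive cabergoline and pasireotide exposure separately from that record. The drug acted on is therefore recoverable. Causality for a non-serious AE without a dose change is not.

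**Step 4. How many patients could be affected**

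Inputs: phase III response at Month 6 of 21/80 = 26.3% on 0.9 mg and 12/82 = 14.6% on 0.6 mg (Protocol 1.2.1); some 65% of patients completed 6 months (Protocol 2.1).

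- High end, every non-responder reaches the combination: 100 − 26.3 = 73.7% and 100 − 14.6 = 85.4%.
- Low end, only completers without response reach it, taking all responders as completers and 65% in both arms: 65 − 26.3 = 38.7% and 65 − 14.6 = 50.4%.

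The range is about 39% to 85% of pasireotide-untreated entrants. If 6 of 64 patients enter on pasireotide, the maximum assumed in Protocol 10.5, 58 are untreated at entry: 58 × 0.387 = 22.4 and 58 × 0.854 = 49.5. Adding the 6 gives about 28 to 56 of 64 patients.

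Timing also varies. Untreated patients who complete both monotherapy steps add cabergoline after the week 17 assessment. Those who cannot go above 0.6 mg can add it without the 0.9 mg step (6.4.1). Patients entering on pasireotide take both drugs from study entry (6.2).

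**The case against.** The best case for the plan has several parts.

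- **The CRF is not supplied.** Section 8.1.1 says what to evaluate; it is not the form. This stands: the finding concerns what the protocol and SAP require and plan, not what the database holds.
- **The glossary is ambiguous.** The sentence quoted above opens by stressing that the relationship of a component should be judged relative to the combination, and Table 6-1 lists the two drugs as separate study treatments. This also stands. It makes 8.1.1 unclear, but it does not turn items 3 and 4 into per-drug items.
- **Other analyses help.** Key safety analyses are planned for the period after cabergoline is added (10.3.1.1), and deaths and SAEs are tabulated by regimen (10.3.1.2). These separate events by time or regimen, not by suspected drug.
- **The gain is modest.** The trial is open-label, non-comparative and exploratory. Per-drug causality would remain unblinded investigator opinion. This limits the value of the change, but the protocol already asks for the same opinion for SAEs and acts on it in Table 6-4.

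A reader might go further and infer that the trial cannot show which drug was reduced, or that AEs on the combination cannot be attributed at all. The dosing record and the per-drug SAE assessment rule out both. A reader might also infer that distinct effects of the two drugs are merged in the tables. AEs are tabulated by preferred term, so different events stand on different rows; only events with the same term share a cell.

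**Conclusion.** The inconsistency is real and limited. The protocol and SAP neither require nor tabulate per-drug causality or action taken for non-serious AEs on the combination, while 6.6, Table 6-4 and 8.2.2 depend on a judgement per drug. The direct conflict with the dose rules covers only non-serious grade 3 or higher events during combination treatment. The documents do not allow the number of such events to be estimated.

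The patients who could be affected are roughly 39% to 85% of untreated entrants plus all who enter on pasireotide. This rests on carrying phase III Month 6 figures over to a different titration scheme. The phase III definition of response also excluded patients whose dose was increased, so the high end may overstate. It would be tempting to say that a large majority is affected from about week 18 onwards, but the figures do not fix the share that tightly, and some patients start the combination much sooner. The inconsistency itself does not depend on these numbers.

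No primary or secondary efficacy result is touched. This is an inexpensive improvement to what the trial can say about combination safety and tolerability.

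**What to change.** 1. **Protocol 8.1.1, items 3 and 4.** Record relationship and action taken separately for pasireotide and cabergoline, matching 8.2.2. Reconcile 6.6, Table 6-4, 8.1.1 and 8.2.2 so that they use the same unit. No view is taken here on any dose rule.
2. **SAP 6.6.1.** For the combination period, split the drug-related, dose adjustment or interruption, and discontinuation tables into pasireotide, cabergoline and either.
3. **For this database.** The latest SAP addendum is dated after database lock, so new form fields can no longer help. First check whether the CRF collected causality per drug. If it did not, derive the drug acted on from the dosing record, tabulate SAE causality per drug from the SAE reports, and state in the study report that causality of other AEs on the combination is at regimen level.

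The cost is two form fields and extra table columns or, with the database locked, one derivation from the dosing pages, one SAE table and a sentence of limitation. The split will produce small cells, and the causality remains unblinded opinion, so the tables should be read as descriptive.
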